Figure 2:	Flowchart of Blinded Dosing Regimen, Study OS440-3004.....	26
Figure 3:	Dosing Schema, Study OS440-3004.....	27

List of Abbreviations and Definitions of Terms

Abbreviation	Definition
AE	Adverse event
AERT	Arbaclofen extended-release tablets
ALT	Alanine transaminase
ANCOVA	Analysis of covariance
AST	Aspartate transaminase
BP	Blood pressure
BUN	Blood urea nitrogen
CFR	Code of Federal Regulations
CGIC	Clinical Global Impression of Change
CRF	Case report form
CRO	Contract Research Organization
C-SSRS	Columbia–Suicide Severity Rating Scale
DSMB	Data Safety Monitoring Board
ECG	Electrocardiogram
eCRF	Electronic case report form
EDSS	Expanded Disability Status Scale
FDA	Food and Drug Administration
GCP	Good Clinical Practices
GFR	Glomerular filtration rate
IB	Investigator’s Brochure
ICF	Informed Consent Form
ICH	International Conference on Harmonization
IEC	Independent Ethics Committee
IND	Investigational New Drug
IRB	Institutional Review Board
IRT	Interactive Response Technology (system)
ITT	Intent-to-treat (population)
LOCF	Last observation carried forward
LSMeans	Least-square means
LUTS	Lower urinary tract symptoms
mAS	Modified Ashworth Scale
MDRD	Modification of Diet in Renal Disease Study
MedDRA	Medical Dictionary for Regulatory Activities
mITT	Modified ITT (population)
MMRM	Mixed model for repeated measures
MS	Multiple Sclerosis
mWOCF	Modified worst observation carried forward
NARCOMS	North American Research Committee on MS
NIMH	National Institute of Mental Health
PGIC	Patient Global Impression of Change
PK	Pharmacokinetic
PMM	Pattern-mixture model
PP	Per-protocol (population)
PT	Preferred term
RBC	Red blood cell
RDC	Remote data capture
REML	Restricted maximum likelihood
RR	Relapsing-remitting (MS)
SAE	Serious adverse event
SAP	Statistical Analysis Plan
SD	Standard deviation
SOC	System organ class

Abbreviation	Definition
SP	Secondary-progressive (MS)
TEAE	Treatment-emergent adverse event
TNmAS-MAL	Total Numeric-transformed mAS score of the most affected limb
USP	Urinary Symptom Profile – USP [®] questionnaire
WBC	White blood cell
WHO	World Health Organization

1 STUDY ADMINISTRATIVE STRUCTURE

2 INTRODUCTION

2.1 Multiple Sclerosis and Spasticity

Multiple Sclerosis (MS) is an acquired inflammatory demyelinating disease of the central nervous system (CNS) that is regarded as the foremost cause of non-traumatic neurologic disability in adults in North America. Multiple Sclerosis has a prevalence of approximately 1 case per 1,000 in the population and a predominance in women (female to male ratio, 2:1). The mean age at onset is 30 years. Although MS is a heterogeneous illness, in 85% of patients it begins with episodic, largely reversible neurologic dysfunction, in a pattern termed relapsing-remitting (RR) MS. In 75% of those patients, the disease advances over time to a steady, irreversible worsening state designated secondary-progressive (SP) MS. Less than 5% of patients have very severe disability (fulminant MS) within the first 5 years after onset, and 10 to 20% of patients remain unimpaired without therapy (benign MS) for 20 years or so.

Clinical manifestations of MS include visual loss, paresthesias, weakness, spasticity, fatigue, and pain. Multiple Sclerosis symptoms may initially wax and wane with the onset and resolution of exacerbations. However, in the latter disease stages, most patients progress to have some permanent disability. Multiple Sclerosis treatment relies on pharmaceutical agents to slow disease progression and reduce the burden of MS symptoms.

Spasticity is a common complication in MS and occurs in up to 84% of patients. The main sign of spasticity is resistance to passive limb movement characterized by increased resistance to stretching, clonus, and exaggerated deep reflexes. The associated features of spasticity, including pain, gait disorders, fatigue, and loss of function, significantly affect patient quality of life. Data collected from the North American Research Committee on MS (NARCOMS) Patient Registry showed that 34% of over 20,000 MS patients surveyed experienced moderate, severe, or total limitation of physical abilities due to spasticity. Consequently, one of the main objectives for the functional management of MS is the symptomatic treatment of spasticity, aiming to improve gait, hygiene, and all the impeded activities of daily living. However, current oral pharmacologic treatments of MS fail in the total control of this problem, both for intolerability or lack of efficacy, defining the unmet medical need for treatment of spasticity.

Baclofen has been in clinical use for more than 35 years and the benefits and risks are well characterized. It is approved for the treatment of spasticity due to MS and spinal cord injury and is a first-line pharmacotherapy as described in the MS Council for Clinical Practice Guidelines for treatment of spasticity in MS. However, the therapeutic potential of baclofen is limited because it is poorly tolerated by patients due to the side effects of sedation, drowsiness, and worsening of fatigue. Therefore, an unmet medical need exists for an effective, better tolerated oral treatment of spasticity.

Baclofen is a racemate (rac-baclofen) consisting of an equal mixture of two enantiomers: the l- or R-enantiomer (arbaclofen) and the d- or S-enantiomer.

Osmotica Pharmaceutical is currently developing arbaclofen extended-release tablets (AERT) for the treatment of spasticity in patients with MS. Arbaclofen is the active R-enantiomer of

baclofen and it has been postulated that the efficacy of baclofen is primarily due to the R-enantiomer. This clinical study aims to demonstrate the clinical efficacy and improved tolerability of AERT in patients with spasticity due to MS.

3 STUDY OBJECTIVES

3.1 Primary Objective

The primary objective of this study is to demonstrate the safety and efficacy of arbaclofen extended-release tablets (AERT) for treatment of spasticity in patients with MS.

4 INVESTIGATIONAL PLAN

4.1 Overall Study Design

This is a multicenter, randomized, double-blind, placebo-controlled, parallel-group study to evaluate the safety and efficacy of oral AERT in MS patients with spasticity. Two doses of AERT, 40 mg and 80 mg, will be compared with placebo. The treatment groups will be randomized in a 1:1:1 ratio. There will be a 9-day titration period, then a 75-day maintenance period, followed by a 7-day taper period. Figure 1 presents the timeline diagram for the study. Figure 2 presents the blinded dosing regimen flowchart, including titration and taper doses, to be used during the study. The dosing schema is presented in Figure 3.

Eligible patients will undergo up to a 21-day washout period for withdrawal of all medications used for anti-spasticity and/or muscle relaxation prior to randomization. A baseline clinical evaluation will be performed (Visit 2) to confirm eligibility for study randomization, and subjects will be randomly assigned to 1 of 3 treatment arms: (1) AERT 40 mg; 2) AERT 80 mg; or 3) placebo. During the first 9 days of drug administration, doses will be titrated every 3 days to a fixed-dose of either AERT 40 mg, AERT 80 mg, or placebo. Subjects will remain at that fixed-dose for 75 days. The co-primary efficacy assessments, changes from baseline in the total numeric-transformed modified Ashworth Scale score of the most affected limb (TNmAS-MAL) and in the Clinical Global Impression of Change (CGIC), will be performed as shown in Table 1. At the end of the maintenance period, the subject's dose will be tapered for an additional 7 days before the subject returns to the site for a final safety evaluation at Day 92 (Visit 6). Table 1 describes the study visits and timing of all study procedures and assessments.

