6 STUDY PROCEDURES

Table 1 and the following subsections present the planned study visits, timing, and details for study procedures. Figure 1 presents the timeline diagram for the study.

As footnoted in Table 1, the TNmAS-MAL assessment will always be performed by the study evaluator (someone other than the investigator) who has been appropriately trained to perform and assess the TNmAS-MAL, and when possible all TNmAS-MAL assessments should be performed for a particular subject by the same study evaluator throughout the study. The TNmAS-MAL assessment should be conducted prior to any scheduled study procedures. The most affected limb will be determined by the study evaluator. The study evaluator must remain blinded to the subject's overall clinical, safety, and CGIC assessments. The investigator or sub-investigator will perform the other assessments (EDSS, C-SSRS) and has access to the findings of the TNmAS-MAL when conducting the CGIC.

Table 1: Schedule of Assessments, Study OS440-3004

Procedure	Screening Visit 1 Days -21 to 0	Baseline Visit 2 Day 1 (±3 days)	Visit 3 Day 10 (±3 days)	Visit 4 Day 42 (±5 days)	Visit 5 Day 84 (±5 days)	Final or Early Termination Visit 6 Day 92 (±5 days)
Written informed consent	X					
Inclusion and exclusion criteria	X	X				
Review study discontinuation criteria		X	X	X	X	
Withdrawal anti-spasticity medication	X					
Assign enrollment number	X					
Randomization		X				
Demography	X					
Medical/surgical history	X					
Physical examination	X					
Height	X					
Weight	X					X
Vital signs ¹	X	X	X	X	X	X
Hematology/serum chemistry/urinalysis	X	X	X	X	X	X
Electrocardiogram	X					X
Pregnancy test ²	X	X	X	X	X	X
Dispense study medication		X	X	X	X	
Collect unused study medication			X	X	X	X
C-SSRS	X	X	X	X	X	X
TNmAS-MAL ³	X	X		X	X	X
EDSS ⁴	X	X				X
CGIC ⁴				X	X	X
PGIC						X
USP [®] questionnaire	X	X	X	X	X	X
Adverse event assessment		X	X	X	X	X
Concomitant medications/therapies	X	X	X	X	X	X

[figure not shown]
C-SSRS = Columbia–Suicide Severity Rating Scale; TNmAS-MAL = Total Numeric-transformed modified Ashworth Scale score of the most affected limb; EDSS = Expanded Disability Status Scale; CGIC = Clinical Global Impression of Change; PGIC = Patient Global Impression of Change; USP = Urinary Symptom Profile.

(footnotes on next page)

Table 1 - Footnotes:

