6.3 Visit 3 – Day 10 (± 3 days)

Assessments/procedures will include the following:

- Review study discontinuation criteria ([Section 12.4](#)).
- Record vital sign measurements, including BP, heart rate, respiratory rate, and body temperature ([Section 9.2](#)).
- Collect blood and urine samples for hematology, serum chemistry, and urinalysis ([Section 9.5](#)).
- Collect a urine sample for pregnancy testing for women of childbearing potential ([Section 7.8](#)).
- Dispense the study medication. The Investigator will explain to the subject how to take the study medication and the regimen to be followed until the next visit ([Section 7.5](#)).
- Collect unused study medication, assess compliance, and study drug accountability ([Section 7.9](#)).
- Administer the C-SSRS ([Section 9.6.3](#)).
- Administer the USP questionnaire ([Section 9.6.2](#)).
- Record any AEs that have occurred ([Section 9.7](#)).
- Record all concomitant medications/therapies the subject is currently taking ([Section 7.7](#)).
- Schedule the next study visit.

6.4 Visit 4 – Day 42 (± 5 days) and Visit 5 – Day 84 (± 5 days)

Assessments/procedures for both visits will include the following:

- Review study discontinuation criteria ([Section 12.4](#)).
- The study evaluator will perform the TNmAS-MAL ([Section 8.1](#)).
- Record vital sign measurements, including BP, heart rate, respiratory rate, and body temperature ([Section 9.2](#)).
- Collect blood and urine samples for hematology, serum chemistry, and urinalysis ([Section 9.5](#)).

- Collect a urine sample for pregnancy testing for women of childbearing potential (Section 7.8).
- Dispense the study medication. The Investigator will explain to the subject how to take the study medication and the regimen to be followed until the next visit (Section 7.5).
- Collect unused study medication, assess compliance, and study drug accountability (Section 7.9).
- Administer the C-SSRS (Section 9.6.3).
- Administer the USP questionnaire (Section 9.6.2).
- Record any AEs that have occurred (Section 9.7).
- Determination of the CGIC by the Investigator (Section 8.2).
- Record all concomitant medications/therapies the subject is currently taking (Section 7.7).
- Schedule the next study visit.

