6.5 Visit 6 (Final Visit or Early Termination) – Day 92 (±5 days)

The assessments/procedures listed for Visit 6 (Final Visit) are to be completed by all subjects regardless of whether they complete the entire study or prematurely withdraw from the study. If the Final Visit is performed before Day 92 due to early termination of the subject, every effort should be made to perform the clinical evaluations as follows, especially the blood sampling for hematology, serum chemistry, and urinalysis, and the ECG. Assessments/procedures will include the following:

- Record weight (Section 9.4).
- The study evaluator will perform the TNmAS-MAL (Section 8.1).
- Record vital sign measurements, including BP, heart rate, respiratory rate, and body temperature (Section 9.2).
- Collect blood and urine samples for hematology, serum chemistry, and urinalysis (Section 9.5). Subject should be fasting if possible.
- Perform a standard 12-lead ECG (Section 9.6.1).
- Collect a urine sample for pregnancy testing for women of childbearing potential (Section 7.8).
- Collect unused study medication, assess compliance, and study drug accountability (Section 7.9).

[figure not shown]
- Administer the C-SSRS (Section 9.6.3).
- Administer the EDSS (Section 8.4).
- Administer the PGIC questionnaire (Section 8.3).
- Administer the USP questionnaire (Section 9.6.2).
- Record any AEs that have occurred (Section 9.7).
- Determination of the CGIC by the Investigator (Section 8.2).
- Record all concomitant medications/therapies the subject is currently taking (Section 7.7).

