7.7 Prior and Concomitant Therapy

The inclusion and exclusion criteria ([Section 5.1](#) and [Section 5.2](#), respectively) provide details on prohibited medications and the permitted duration since their last use prior to Screening and/or study drug administration. All medications taken within 90 days before Visit 2/Baseline (randomization) are to be recorded in the CRF/eCRF. Eligible patients will undergo up to a 21-day washout period (no drug onboard) for withdrawal of all medications used for anti-spasticity and/or muscle relaxation prior to randomization (see Inclusion Criterion 6). Subjects will be ineligible for randomization if they concomitantly use any of the medications listed in Appendix 6 (see Exclusion Criterion 5). Table 3 presents the half-life, taper period, and washout period for specific anti-spasticity and/or muscle relaxation medications. Tapering of an existing anti-spasticity drug depends on the dose of the drug and other conditions. The investigator should use medical judgment to safely taper the dose. Under most conditions, the taper should take no more than 2 weeks. For anti-spasticity medications not shown in Table 3, please contact the medical monitor for discussions of the washout period.

Table 3: Taper and Washout Periods for Specific Anti-spasticity and/or Muscle Relaxation Medications, Study OS440-3004

Drug	Half-Life (hours)	Taper Period	Washout Period
Baclofen	3 to 5	3 to 14 days	1 day
Clonidine	12 to 16	3 to 14 days	3 days
Dantrolene	8 to 9	3 to 14 days	2 days
Gabapentin	5 to 7	3 to 14 days	2 days
Zanaflex	3	3 to 14 days	1 day
Diazepam	100	3 to 14 days	3 weeks

All conventional medications regularly used for the treatment of MS, other than anti-spasticity medications, and non-pharmacological therapies (intended to alleviate spasticity, eg, physiotherapy) are allowed provided they have been taken/administered for at least 1 month prior to enrollment and no dose adjustments are expected for the duration of this study.

Changes in either the dose or frequency of concomitant medications taken for the treatment of MS should not be made for the duration of this study. In the event a dose adjustment is needed for a concomitant medication, the Investigator will contact the Sponsor to determine if the subject may remain in the study or needs to be withdrawn.

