11.4.2 Secondary Efficacy Endpoints

Secondary efficacy endpoints include:

- EDSS
- PGIC
- TNmAS – Total Limbs

Secondary efficacy endpoints will be summarized descriptively and analyzed using the same type of MMRM analysis used for the co-primary efficacy endpoints. Pairwise comparisons between the AERT doses and placebo will be provided at each visit where data are collected. Additional factors along with interaction terms may be included in the models as sensitivity analyses. Details will be provided in the SAP.

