Appendix 4. Patient Global Impression of Change Scale

PATIENT'S GLOBAL IMPRESSION OF CHANGE (PGIC) SCALE

Date _____ Patient Name _____ Date of Birth _____

Chief Complaint (Presenting Problem): _____

Since beginning treatment at this clinic, how would you describe the change (if any) in ACTIVITY LIMITATIONS, SYMPTOMS, EMOTIONS, and OVERALL QUALITY OF LIFE, related to your painful condition? Please circle the number below, that matches your degree of change since beginning care at this clinic for the above stated chief complaint.

No change	Almost the same	A little better	Somewhat better	Moderately better	Better	A great deal better
1	2	3	4	5	6	7

Explanation:

- 1 = No change (or condition has got worse)
- 2 = Almost the same, hardly any change at all
- 3 = A little better, but no noticeable change
- 4 = Somewhat better, but the change has not made any real difference
- 5 = Moderately better, and a slight but noticeable change
- 6 = Better, and a definite improvement that has made a real and worthwhile difference
- 7 = A great deal better, and a considerable improvement that has made all the difference

Patient's signature: X _____

Do not write in this box - FOR OFFICE USE ONLY.

NOTE TO HEALTH CARE PROVIDER

A significant, favorable change is a score of 5- 7
No significant change is a 1-4 response.
Note, this is a dichotomous scale (5-7 = yes; 1-4 = no).
A 2-point change is significant from their last reported score.
Reference: Hurst H, Bolton J. Assessing the clinical significance of change scores recorded on subjective outcome measures. Journal of Manipulative Physiological Therapeutics (JMPT) 2004;27:26-35.

[figure not shown]

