7.3.3. Handling of Early Termination Visit Information

If a subject is terminated early from this study the early termination visit data will be analyzed at the closest scheduled visit. If the closest visit has valid data, the early termination data will be assigned to the next available visit.

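### For completers, PGIC, the only patient-rated efficacy endpoint, is collected only after the taper, and the SAP assigns it to a model whose visits do not include that one

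*Protocol*

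**What the plan says.** Protocol Section 4.1 sets out 9 days of titration, 75 days on the fixed dose and 7 days of taper. It then says that the subject's "dose will be tapered for an additional 7 days before the subject returns to the site for a final safety evaluation", which is Visit 6 at Day 92.

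Table 1 in the protocol and Table 1 in the SAP agree on the schedule. PGIC is marked at Visit 6 only. EDSS is marked at Screening, Baseline and Visit 6. CGIC and TNmAS-MAL are marked at Visits 4, 5 and 6, and TNmAS-MAL also before treatment. The procedure lists match the tables. The shared list for Visits 4 and 5 in Section 6.4 ("Assessments/procedures for both visits will include the following") contains neither PGIC nor EDSS. The Visit 6 list in Section 6.5 contains both, including "Administer the PGIC questionnaire".

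PGIC and EDSS are secondary efficacy endpoints (Protocol 11.4.2, SAP 9.2.1). SAP 9.2.2 gives PGIC the CGIC model and EDSS the TNmAS-MAL model. In SAP 9.1.2 the visit factor of both models is Visit 4 and Visit 5. Protocol 11.4.2 and SAP 9.2.2 also state: "Pairwise comparisons between the AERT doses and placebo will be provided at each visit where data are collected". For early withdrawals, SAP 7.3.3 says: "If a subject is terminated early from this study the early termination visit data will be analyzed at the closest scheduled visit".

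**The concern.** The treatment is symptomatic, and the trial asks whether it helps at a fixed daily dose. The plan puts efficacy inference for the co-primary endpoints on the two maintenance visits, although both are collected at Visit 6 as well. PGIC gets the reverse: it is collected only at the visit that Section 4.1 describes as a safety evaluation, after the dose has been withdrawn.

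If some benefit fades during the taper, the PGIC difference between AERT and placebo shrinks. A null PGIC could then be read as patients noticing no benefit, although completers were never asked while on the maintenance dose.

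Subjects who withdraw early complete the Visit 6 assessments when they leave. Their drug exposure at that point differs from a completer's: possibly nearer the full dose, possibly several days after stopping. SAP 9.1.3 itself allows for more discontinuations at 80 mg, so the mix of exposures could differ by arm.

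The SAP also leaves the PGIC analysis time point unsettled, because the assigned model and the PGIC schedule have no visit in common.

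**Working it through.** **Inputs.** Period lengths of 9, 75 and 7 days (Protocol 4.1). Visit 6 at Day 92 ± 5 (Protocol Table 1 and 6.5). Scale schedules (Table 1 in both documents). Maximal cumulative doses of 3320 mg and 6580 mg (Protocol Table 2). Model visits (SAP 9.1.2).

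**1. Reproduce the plan's Day 92.** Last fixed-dose day = 9 + 75 = Day 84. Last taper day = 84 + 7 = Day 91. The next day is Day 92, as stated.

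**2. Nominal gaps at Visit 6.** From the last fixed dose: 92 − 84 = 8 days. From the last taper dose: 92 − 91 = 1 day.

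**3. Across the window.** Days 92 − 5 = 87 to 92 + 5 = 97. Gap from Day 84: 87 − 84 = 3 to 97 − 84 = 13 days. A visit on Days 87 to 91 falls inside the taper. A visit on Days 92 to 97 is 1 to 6 days after the last taper dose (92 − 91, 97 − 91). No day in the window is on the fixed dose. This assumes that dosing starts on Day 1, that the fixed dose lasts exactly 75 days and that the taper starts on Day 85.

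**4. Dose outside maintenance.** 40 mg arm: 3320 − 75 × 40 = 320 mg over 9 + 7 = 16 days, a mean of 20 mg/day. 80 mg arm: 6580 − 75 × 80 = 580 mg over 16 days, a mean of 36.25 mg/day. The split between titration and taper is in figures that are not shown, so the dose just before Visit 6 is unknown.

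**5. Who rates what.** TNmAS is rated by the study evaluator (Protocol 8.1), CGIC by the investigator (8.2) and EDSS from a neurologist's examination (8.4). USP is completed by the patient but is a safety measure (Section 9). PGIC is therefore the only patient-rated efficacy endpoint.

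**6. Ratings scheduled for completers.**

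| Endpoint | Post-baseline ratings on the fixed dose | Post-taper rating (Visit 6) |
|---|---|---|
| TNmAS-MAL | 2 (Days 42, 84) | 1 |
| CGIC | 2 (Days 42, 84) | 1 |
| PGIC | 0 | 1 |
| EDSS | 0 | 1 |

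**7. Model against schedule.** The CGIC model has visit levels Visit 4 and Visit 5. PGIC is scheduled at Visit 6. The overlap is empty.
- Read literally with SAP 7.3.3, the only PGIC values that could fall at Visit 4 or 5 come from early terminators, and no completer contributes.
- Read through the statement about comparisons wherever data are collected, the analysis is at Visit 6. There is then one post-baseline visit, so the visit term, the interaction and the unstructured covariance have no role. The SAP does not say whether early-termination ratings join that analysis or move to an earlier visit.

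**8. Size of the dilution.** If a fraction f of the on-dose PGIC difference remains at Visit 6, the expected observed difference is f times the on-dose difference. The documents give no AERT half-life, time to loss of effect, visible taper dose or PGIC effect size. Nothing in them narrows f within 0 to 1.

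**The case against.** **Dilution is not shown to be likely.** A reader might infer that it is, from Table 3 in Protocol 7.7 ("Table 3 presents the half-life, taper period, and washout period for specific anti-spasticity and/or muscle relaxation medications"). Its baclofen row gives a half-life of 3 to 5 hours and a 1-day washout, and arbaclofen is the active enantiomer of baclofen. The documents do not support that step. The row concerns prior baclofen before randomization, not AERT, which is extended-release with no stated half-life. Other text is stricter: Protocol 6.2 asks for at least 14 days of abstinence before baseline, and SAP 5.1 gives a washout of at least 14 days. Dilution is possible, and no more can be said.

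**PGIC looks back.** The form in Appendix 4 asks: "Since beginning treatment at this clinic, how would you describe the change". A patient seen one day after the last taper dose can draw on the whole treatment period. This stands and limits the likely loss, but the answer is still given after withdrawal.

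**The 8 days are not drug-free.** Reduced doses continue to about Day 91, and a visit early in the window falls within the taper. This stands.

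**EDSS.** A reader might extend the harm to EDSS, which has the same schedule and the same model mismatch. The documents do not show that EDSS gains or loses a short-term symptomatic effect, so no harm is claimed.

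**Little rides on it.** Success depends on TNmAS-MAL and CGIC at Day 84. Dilution toward no difference would not in itself produce a false claim of benefit. CGIC already gives an on-dose global rating, though from the investigator. All of this stands, and it limits the weight of the point.

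**A rationale may exist.** The protocol text between Section 4.1 and Section 5 was not available to this review, so its silence is not counted against the plan. A rationale would not create an on-dose rating or settle the model visits.

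**Conclusion.** The point holds in a limited form. Completers are scheduled for no PGIC rating on the maintenance dose. Their only rating is post-taper, nominally 8 days after the last fixed dose and 1 day after the last reduced dose, or 3 to 13 days after Day 84 across the window under the dosing assumptions above. Any treatment difference on PGIC may be diluted by an amount that cannot be computed. Completers and early terminators are rated under different exposure, and SAP 9.2.2 names a model whose visits do not include the PGIC visit.

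The documents do not support saying that a null PGIC is the expected result, or that EDSS is harmed. The co-primary analyses are untouched, and PGIC lies outside the testing sequence in SAP 7.5. What is at stake is how the one patient-reported efficacy result can be interpreted. The correction is cheap enough to be worth making.

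**What to change.** - **Schedule.** Add PGIC at Visit 5 (Day 84), before the first taper dose: one mark in Table 1 of each document, and one item in Protocol 6.4 labelled as Visit 5 only, because that list also serves Visit 4. Keep PGIC at the early termination visit.
- **SAP 9.2.2.** Name Day 84 as the PGIC time point, with a single-visit model (treatment and study center; like CGIC, PGIC has no baseline value). State which early-termination ratings enter that analysis and how SAP 7.3.3 applies to them. Label any Visit 6 PGIC as post-taper.
- **If subjects have already passed Visit 5.** State in the SAP that Visit 6 PGIC is a post-taper rating and does not estimate the maintenance-dose effect.
- **EDSS.** It is enough to name Visit 6, post-taper, as its analysis time point. Moving it to Visit 5 is optional.

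**Cost.** A protocol amendment with IRB/IEC approval (Protocol 12.2), a short revision of SAP Table 1 and 9.2.2, and one brief questionnaire at a visit subjects already attend.
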